Reference Drug 1	Mircera® — methoxy polyethylene glycol-epoetin beta (F. Hoffmann-La Roche Ltd., Switzerland) solution for intravenous and subcutaneous injection
Reference Drug 2	Aranesp® — darbepoetin alfa (Amgen Europe B.V., Netherlands), solution for injections
Population:	Healthy male volunteers aged 18 to 45 years
Study Sponsor:	JSC BIOCAD, Russia.  Postal address: [name]. [contact], [contact].  Legal address: [name]
Study Aims and Objectives	
Study aim: To evaluate the tolerability, safety, pharmacokinetics, pharmacodynamics and immunogenicity of single ascending doses of BCD-131 in healthy volunteers as compared to Mircera® and Aranesp®.
 
Study objectives (Stage I):
 

1. Establish the frequency and severity of adverse events following the administration of single ascending doses of BCD-131 to healthy volunteers.

2. Establish key pharmacokinetic (PK) parameters (<math>AUC_{0-1176\text{ h}}</math>, <math>AUC_{0-\infty}</math>, <math>C_{\max}</math>, <math>T_{\max}</math>, <math>T_{1/2}</math>, <math>K_{\text{el}}</math> and <math>CL</math>) of BCD-131 following the administration of single ascending doses of the drug product to healthy volunteers.

	

3. Establish pharmacodynamic (PD) parameters (<math>AUEC_{0-1176\text{ h}}</math>, <math>AC-E_{max}</math>) of BCD-131 based on the absolute reticulocyte count and Hb values in the blood of healthy volunteers following the administration of single ascending doses of BCD-131.

4. Study serum levels of binding antibodies (BAbs) in the blood of healthy volunteers following the subcutaneous administration of single ascending doses of BCD-131.

5. Establish main PK (<math>AUC_{0-1176\text{ h}}</math>, <math>AUC_{0-\infty}</math>, <math>C_{max}</math>, <math>T_{max}</math>, <math>T_{1/2}</math>, <math>K_{el}</math> and CL) and PD parameters (<math>AUEC_{0-1176\text{ h}}</math>, <math>AC-E_{max}</math> based on changes in the absolute reticulocyte count and Hb levels in the blood) as well as immunogenicity of therapeutic doses of Mircera® and Aranesp® given as subcutaneous injections to healthy volunteers.

6. Establish a safe dose of subcutaneous BCD-131 to be used at stage II of the study.

Study objectives (Stage II):	

1. Establish key pharmacokinetic parameters (<math>AUC_{0-1176\text{ h}}</math>, <math>AUC_{0-\infty}</math>, <math>C_{max}</math>, <math>T_{max}</math>, <math>T_{1/2}</math>, <math>K_{el}</math> and CL) of BCD-131 given as a single subcutaneous or intravenous injection to healthy volunteers at a dose established at stage I of the study.

2. Establish key pharmacodynamic parameters (<math>AUEC_{0-1176\text{ h}}</math>, <math>AC-E_{max}</math> based on changes in the absolute reticulocyte count and Hb levels in the blood) of BCD-131 given as a single subcutaneous or intravenous injection to healthy volunteers at a dose established at stage I of the study.

3. Establish the frequency and severity of adverse events and evaluate the level of BAbs to BCD-131 given as a single subcutaneous or intravenous injection to healthy volunteers at a dose established at stage I of the study.

4. Establish subcutaneous and intravenous doses of BCD-131 to be used in a phase II clinical study.

Study Design:	
Stage I
 
Stage I of clinical study BCD-131-1 is an open-label, non-randomized clinical study of pharmacokinetics, pharmacodynamics, tolerability, safety and immunogenicity of the novel drug product given to healthy volunteers at ascending doses (Phase 1, a traditional “3+3” design). Also, at stage I the investigators will evaluate the PK and PD parameters of the closest analogues of BCD-131 (Mircera® and Aranesp®) given as subcutaneous injections at therapeutic doses.
 
Volunteers (no more than 54 subjects at stage I) will be included in the study after they have signed an informed consent form, completed an examination at screening (no more than 14 days) and received the approval of the investigator confirming their eligibility for the study.

	
Evaluation of pharmacokinetics, pharmacodynamics and safety of ascending doses of BCD-131
 
The evaluation of pharmacokinetics, safety and tolerability of BCD-131 will be conducted in 8 cohorts:
 

1. Cohort 01 will include no more than 6 volunteers who will receive a single subcutaneous injection of BCD-131 at a dose of 0.05 µg/kg body weight.

2. Cohort 02 will include no more than 6 volunteers who will receive a single subcutaneous injection of BCD-131 at a dose of 0.15 µg/kg body weight.

3. Cohort 03 will include no more than 6 volunteers who will receive a single subcutaneous injection of BCD-131 at a dose of 0.40 µg/kg body weight.

4. Cohort 04 will include no more than 6 volunteers who will receive a single subcutaneous injection of BCD-131 at a dose of 1.05 µg/kg body weight.

5. Cohort 05 will include no more than 6 volunteers who will receive a single subcutaneous injection of BCD-131 at a dose of 1.70 µg/kg body weight.

6. Cohort 06 will include no more than 6 volunteers who will receive a single subcutaneous injection of BCD-131 at a dose of 2.75 µg/kg body weight.

7. Cohort 07 will include no more than 6 volunteers who will receive a single subcutaneous injection of BCD-131 at a dose of 4.45 µg/kg body weight.

 
Volunteers will be included in the study in a consecutive order. First, three volunteers will be included in Cohort 01 to receive a single subcutaneous injection of BCD-131 at a calculated starting safe dose of 0.05 µg/kg. If during 14 days after the injection these volunteers do not develop any treatment-emergent Grade 3–4 adverse events, the next three volunteers will be included in the study (Cohort 02). The further inclusion algorithm is as follows:
 
If during 14 days after the injection of BCD-131 the subjects do not develop any treatment-emergent Grade 3-4 AEs (DLT), the next cohort consisting of three volunteers will be included in the study to receive an escalated dose of BCD-131 (Cohort 03, Cohort 04, Cohort 05 etc.).
 
If during 14 days after the injection of BCD-131 only one volunteer (of three) develops a treatment-emergent Grade 3-4 AE (DLT), three more healthy volunteers will be included in this cohort to receive BCD-131.

--	--

	
If two subjects develop treatment-emergent Grade 3-4 AEs (DLT), the dose of BCD-131 which resulted in these events is considered to be the maximum tolerated dose (MTD). No further dose escalating is performed.
 
Thus, the dose-limiting toxicity is assessed as close as possible to the time of drug administration during the first 14 days after the injection. However, follow-up of volunteers does not stop; it will continue up to Day 50 from the moment of injection and include the monitoring of volunteers' health as well as safety and PK parameters of BCD-131.
 
Evaluation of pharmacokinetics, pharmacodynamics and safety of subcutaneous therapeutic doses of Mircera® and Aranesp®
 
Simultaneously with the evaluation of pharmacokinetics, pharmacodynamics and safety of ascending doses of BCD-131, the investigators will evaluate the pharmacokinetics, pharmacodynamics and safety of subcutaneous therapeutic doses of Mircera® and Aranesp®. For this purpose, 12 more volunteers will be included in the study.
 
After having been randomized in a 1:1 ratio, the volunteers will be assigned to 2 groups. Six volunteers in Group 1 will receive a single subcutaneous injection of Mircera® at a dose of 1.20 µg/kg (Day 1). Six volunteers in Group 2 will receive a single subcutaneous injection of Aranesp® at a dose of 0.45 µg/kg (Day 1).
 
After the last volunteer enrolled in stage I of the study has completed all the procedures specified in the Study Protocol, an interim analysis of the data obtained will be performed. Based on the comparison of pharmacokinetics, pharmacodynamics and safety of different doses of the test drug and active comparators, the investigators will establish a dose of BCD-131 which ensures PD effects similar to those of the closest analogues (Mircera®, Aranesp®) given as subcutaneous injections at therapeutic doses. The established dose of BCD-131 will be used at stage II of the study.

--	---

	
Subjects will be asked to stay at the study site for the first 24 h after the injection because multiple blood samples are to be collected over this period.
 
Regardless of the group/cohort to which a volunteer has been assigned, s/he will be followed-up for 50 days during which 16 visits will be performed.
 
Stage II
 
Stage II of the study aims to further evaluate pharmacokinetics, pharmacodynamics and safety of subcutaneous and intravenous injections of BCD-131 at a dose which ensures PD effects similar to those of the closest analogues (Mircera®, Aranesp®) given as subcutaneous injections at therapeutic doses. For this purpose, 12 volunteers will be included in the study after they have signed an informed consent form, completed an examination at screening (no more than 14 days) and received the approval of the investigator confirming their eligibility for the study.
 
After having been randomized in a 1:1 ratio, the volunteers will be assigned to 2 groups.
 

• Six volunteers in Group 1 will receive a single intravenous injection of BCD-131 at a dose established at stage I of the study (Day 1).

• Six volunteers in Group 2 will receive a single subcutaneous injection of BCD-131 at a dose established at stage I of the study (Day 1).

 
Subjects will be asked to stay at the study site for the first 24 h after the injection because multiple blood samples are to be collected over this period. Regardless of the group/cohort to which a volunteer has been assigned, s/he will be followed-up for 50 days during which 16 visits will be performed.

Use of BCD-131 at Stage I	
The test drug and reference drugs will be used in accordance with the study design:
 
Evaluation of pharmacokinetics, pharmacodynamics and safety of ascending doses of BCD-131

	

1. Cohort 01 will include no more than 6 volunteers who will receive a single subcutaneous injection of BCD-131 at a dose of 0.05 µg/kg body weight.

2. Cohort 02 will include no more than 6 volunteers who will receive a single subcutaneous injection of BCD-131 at a dose of 0.15 µg/kg body weight.

3. Cohort 03 will include no more than 6 volunteers who will receive a single subcutaneous injection of BCD-131 at a dose of 0.40 µg/kg body weight.

4. Cohort 04 will include no more than 6 volunteers who will receive a single subcutaneous injection of BCD-131 at a dose of 1.05 µg/kg body weight.

5. Cohort 05 will include no more than 6 volunteers who will receive a single subcutaneous injection of BCD-131 at a dose of 1.70 µg/kg body weight.

6. Cohort 06 will include no more than 6 volunteers who will receive a single subcutaneous injection of BCD-131 at a dose of 2.75 µg/kg body weight.

7. Cohort 07 will include no more than 6 volunteers who will receive a single subcutaneous injection of BCD-131 at a dose of 4.45 µg/kg body weight.

 
Evaluation of pharmacokinetics, pharmacodynamics and safety of subcutaneous therapeutic doses of Mircera® and Aranesp®
 
Group 1: Six volunteers will receive a single subcutaneous injection of Mircera® at a dose of 1.20 µg/kg.
 
Group 2: Six volunteers will receive a single subcutaneous injection of Aranesp® at a dose of 0.45 µg/kg.

Use of BCD-131 at Stage II	BCD-131 will be used in accordance with the study design:  Group 1: Six volunteers will receive a single intravenous injection of BCD-131 at a dose established at stage I of the study.  Group 2: Six volunteers will receive a single subcutaneous injection of BCD-131 at a dose established at stage I of the study.
Time Points for Blood Sampling to Evaluate PK at Stage I of the Study	In the groups of volunteers receiving BCD-131 and Mircera®, blood sampling for the PK evaluation will be performed as follows: 

1. PK1-1 — 5 min before the injection of BCD-131/Mircera®

2. PK2-1 — 30 ± 5 min after the injection of BCD-131/Mircera®

3. PK3-1 — 2 h ± 10 min after the injection of BCD-131/Mircera®

4. PK4-1 — 8 h ± 15 min after the injection of BCD-131/Mircera®

5. PK5-1 — 24 h ± 20 min after the injection of BCD-131/Mircera®

6. PK6-1 — 48 h ± 30 min after the injection of BCD-131/Mircera®

	

7. PK7-1 — 72 h ± 30 min after the injection of BCD-131/Mircera®

8. PK8-1 — 96 h ± 60 min after the injection of BCD-131/Mircera®

9. PK9-1 — 120 h ± 60 min after the injection of BCD-131/Mircera®

10. PK10-1 — 168 h ± 60 min after the injection of BCD-131/Mircera®

11. PK11-1 — 216 h ± 120 min after the injection of BCD-131/Mircera®

12. PK12-1 — 288 h ± 120 min after the injection of BCD-131/Mircera®

13. PK13-1 — 336 h ± 120 min after the injection of BCD-131/Mircera®

14. PK14-1 — 504 h ± 120 min after the injection of BCD-131/Mircera®

15. PK15-1 — 672 h ± 120 min after the injection of BCD-131/Mircera®

16. PK16-1 — 840 h ± 120 min after the injection of BCD-131/Mircera®

17. PK17-1 — 1008 h ± 120 min after the injection of BCD-131/Mircera®

18. PK18-1 — 1176 h ± 120 min after the injection of BCD-131/Mircera®

--	---

In the group of volunteers receiving Aranesp®, blood sampling for the PK evaluation will be performed as follows:

1. PK1-1 — 5 min before the injection of Aranesp®
2. PK2-1 — 30 ± 5 min after the injection of Aranesp®
3. PK3-1 — 2 h ± 10 min after the injection of Aranesp®
4. PK3-1 — 8 h ± 15 min after the injection of Aranesp®
5. PK5-1 — 16 h ± 20 min after the injection of Aranesp®
6. PK6-1 — 24 h ± 20 min after the injection of Aranesp®
7. PK7-1 — 36 h ± 30 min after the injection of Aranesp®
8. PK8-1 — 48 h ± 30 min after the injection of Aranesp®
9. PK9-1 — 72 h ± 30 min after the injection of Aranesp®
10. PK10-1 — 96 h ± 60 min after the injection of Aranesp®
11. PK11-1 — 120 h ± 60 min after the injection of Aranesp®
12. PK12-1 — 168 h ± 60 min after the injection of Aranesp®
13. PK13-1 — 216 h ± 120 min after the injection of Aranesp®
14. PK14-1 — 288 h ± 120 min after the injection of Aranesp®
15. PK15-1 — 336 h ± 120 min after the injection of Aranesp®
16. PK16-1 — 504 h ± 120 min after the injection of Aranesp®
17. PK17-1 — 672 h ± 120 min after the injection of Aranesp®
18. PK18-1 — 840 h ± 120 min after the injection of Aranesp®
19. PK19-1 — 1008 h ± 120 min after the injection of Aranesp®
20. PK20-1 — 1176 h ± 120 min after the injection of Aranesp®

Time Points for Blood Sampling to Evaluate PK at Stage II of the Study	

1. PK1-2 — 5 min before the injection of BCD-131

2. PK2-2 — 15 ± 3 min after the injection of BCD-131

3. PK3-2 — 30 ± 5 min after the injection of BCD-131

4. PK4-2 — 60 ± 5 min after the injection of BCD-131

5. PK5-2 — 2 h ± 10 min after the injection of BCD-131

6. PK6-2 — 4 h ± 15 min after the injection of BCD-131

7. PK7-2 — 8 h ± 15 min after the injection of BCD-131

8. PK8-2 — 24 h ± 20 min after the injection of BCD-131

9. PK9-2 — 48 h ± 30 min after the injection of BCD-131

10. PK10-2 — 72 h ± 30 min after the injection of BCD-131

11. PK11-2 — 96 h ± 60 min after the injection of BCD-131

12. PK12-2 — 120 h ± 60 min after the injection of BCD-131

13. PK13-2 — 168 h ± 60 min after the injection of BCD-131

14. PK14-2 — 216 h ± 120 min after the injection of BCD-131

15. PK15-2 — 288 h ± 120 min after the injection of BCD-131

16. PK16-2 — 336 h ± 120 min after the injection of BCD-131

17. PK17-2 — 504 h ± 120 min after the injection of BCD-131

18. PK18-2 — 672 h ± 120 min after the injection of BCD-131

19. PK19-2 — 840 h ± 120 min after the injection of BCD-131

20. PK20-2 — 1008 h ± 120 min after the injection of BCD-131

21. PK21-2 — 1176 h ± 120 min after the injection of BCD-131

Planned Sample Size:	Up to 66 healthy volunteers
Inclusion Criteria:	

1. Signing of the Informed Consent Form;

2. Male sex;

3. Age of 18 to 45 years, inclusive;

4. BMI within normal limits (18.5–24.9 kg/m^2);

5. Healthy patients, which is proved by their medical history, physical examination and laboratory findings:

• No clinically significant abnormalities of circulatory, respiratory, nervous, hematopoietic, endocrine and digestive systems, liver and kidneys in the past medical history and at screening;

• No history of cardiovascular disorders or thyroid disorders;

• No history of hematologic disorders, including but not limited to any type of anemia, myelodysplastic syndrome, blood cancers, hemolytic syndrome, hemoglobinopathies, coagulopathies;

• CBC results within normal limits, including:

◦ Hemoglobin within 132–173 g/L;

◦ Hematocrit (based on CBC results) within 39–49%;

◦ Platelet count within 150–400*10^9/L;

◦ Absolute reticulocyte count within 30.4–93.5 * 10^9/L;

• Blood biochemistry and urinalysis results within normal limits;

	

• Serum ferritin within 20–250 µg/L;

• Serum endogenous erythropoietin within 4.3–29.0 MIU/mL;

• Hemodynamic parameters within normal limits: systolic blood pressure within 100–139 mmHg; diastolic blood pressure within 60–90 mmHg; heart rate within 50–90 bpm;

• No history of chronic infections (tuberculosis) or chronic inflammation;

• No hepatitis B or C, HIV, or syphilis;

• No acute infections within 4 weeks prior to inclusion in the study;

• No psychiatric disorders and other conditions (including depression) that can interfere with the volunteer's ability to follow the study protocol;

• Well-being (in the volunteer's opinion) within 30 days prior to inclusion in the study;

 

6. No history of or current (at baseline) alcohol or drug abuse;

7. Ability of the volunteer, in the investigator's opinion, to follow the study protocol procedures;

8. Willingness of volunteers and their sexual partners with preserved reproductive potential to use reliable contraception within 2 weeks before inclusion in the study and up to 7 weeks after the injection of the test product. This criterion is not applicable to subjects who underwent surgical sterilization. Reliable methods of contraception include one barrier method in combination with one of the following methods: spermicides, intrauterine device/oral contraceptives (for sexual partners).

9. Willingness of volunteers to avoid alcohol intake within 24 hours before and 8 days after each injection of the test drug;

Exclusion Criteria:	

1. History of treatment with erythropoietins or any other ESAs;

2. Acute bleeding, blood/plasma donation or blood transfusion within 2 months before inclusion in the study;

3. History of chronic bleeding;

4. Standard laboratory and instrumental findings outside normal limits at screening;

5. History of allergies (anaphylactic shock or multiple drug allergy syndrome);

6. Known allergy or intolerance to any components of the investigational product;

7. Major surgery within 30 days prior to screening, or surgery being scheduled for any time during the study;

8. Impossibility to install a venous catheter for blood sampling (e.g. because of skin disorders at the sites of venipuncture);

9. Diseases or other conditions that can interfere with the pharmacokinetics of the investigational drug (e.g. chronic liver, kidney, blood, circulatory system, lung or neuroendocrine diseases, including diabetes mellitus and others);

	

10. History of fever of 40 °C or more;

11. History of elevated hepatic transaminases (above 2.5xULN);

12. Episodes of thrombosis and/or thromboembolia in past medical history (myocardial infarction, stroke, transient ischemic attacks, deep vein thrombosis, pulmonary embolism within 6 months prior to inclusion in the study) as well as an increased risk of deep vein thrombosis;

13. History of epileptic attacks or seizures;

14. History or current (at screening) depression, suicidal thoughts/ attempts;

15. Regular oral or parenteral use of any medications including over-the-counter drugs, vitamins and nutritional additives within 2 weeks before a scheduled injection of the test drug;

16. Use of drugs, including OTC products, that significantly affect the hemodynamics, hepatic function, etc. (barbiturates, omeprazole, cimetidine, etc.) within 30 days before a scheduled injection of the test drug;

17. Vaccination within 4 weeks before a scheduled injection of the test drug;

18. Smoking more than 10 cigarettes per day;

19. Consumption of more than 10 portions of alcohol per week (one portion equals to 0.5 L of beer, 200 mL of wine or 50 mL of ethanol) or a history of alcohol, drug or medication abuse;

20. Participation in other clinical studies within 1 month before screening or simultaneous participation in another clinical study;

21. Previous participation in this study.

Overall Duration of the Study:	The expected duration of the study is 12 months, including the periods of enrollment, screening, treatment and follow-up as well as data collection and statistical analysis of the results. Each subject is expected to participate in the study for no more than 64 days, including the screening period (up to 2 weeks) and the active phase of the study (50 days).
Endpoints to Evaluate Single-Dose PK:	Primary: 

✓ AUC0-1176 h (area under the concentration vs. time curve from the moment of injection to 1176 h [Day 50 of follow-up]) and AUC0-∞ (to infinity).

 Secondary: 

✓ Cmax (maximum serum concentration),

✓ Tmax (time to Cmax),

✓ T½ (half-life),

✓ Kel (elimination constant),

✓ CL (total clearance).

PD Endpoints	Primary:

	

✓ AUEC0-1176 h (total area under the effect vs. time curve from the moment of injection to 1176 h [Day 50 of follow-up]) based on the change in the absolute reticulocyte count after a single-dose injection of the drug product.

✓ AC-Emax (absolute maximum increase in the test parameter vs. baseline) based on the change in the absolute reticulocyte count in the blood after a single-dose injection of the drug product.

 
Secondary:
 

✓ AUEC0-1176 h (total area under the effect vs. time curve from the moment of injection to 1176 h [Day 50 of follow-up]) based on the change in the Hb level in the blood after a single-dose injection of the drug product.

✓ AC-Emax (absolute maximum increase in the test parameter vs. baseline) based on the change in the Hb level in the blood after a single-dose injection of the drug product.

												
Endpoint for Pain Assessment	

✓ The average VAS score evaluating the pain during the injection.

												
Safety Endpoints:	

✓ Total SAEs.

✓ Total AEs.

✓ Incidence of administration site reactions.

✓ Incidence of Grade 3-4 AEs and SAEs.

✓ Frequency of early withdrawals due to AEs and SAEs.

												
Immunogenicity Endpoints	

✓ Incidence of BAbs to the drug product on Day 50 from the moment of a single-dose injection of the drug.

												
Statistical Analysis	
Sample size calculation
 
The sample size for the study was calculated based on the “3+3” design used in the study of doses and additional test parameters:
 

Cohort	Dose, µg/kg	Number of volunteers to be enrolled (obligatory)	Number of volunteers who can be enrolled if DLT signs develop	

01	0.05	3	3	

02	0.15	3	3	

	Cohort	Dose, µg/kg	Number of volunteers to be enrolled (obligatory)	Number of volunteers who can be enrolled if DLT signs develop	01	0.05	3	3	02	0.15	3	3
Cohort	Dose, µg/kg	Number of volunteers to be enrolled (obligatory)	Number of volunteers who can be enrolled if DLT signs develop										
01	0.05	3	3										
02	0.15	3	3										

	03	0.40	3	3
	04	1.05	3	3
	05	1.70	3	3
	06	2.75	3	3
	07	4.45	3	3

To assess the PK and PD of the closest analogues of BCD-131, 6 more volunteers will be included in the study to receive Mircera® and 6 more volunteers will be enrolled to receive Aranesp®.

To assess the PK and PD of BCD-131 given as a subcutaneous or intravenous injection at a dose established at stage I of the study, 6 more volunteers will be included in the study to receive BCD-131 as an intravenous injection and 6 more volunteers will be enrolled to receive BCD-131 as a subcutaneous injection.

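### The dose at which two subjects have DLTs is labelled the MTD, although in the traditional 3+3 design that the plan names, that dose has exceeded the MTD

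*Protocol*

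**What the plan says.** The Study Design section of the protocol synopsis describes stage I as giving BCD-131 "at ascending doses (Phase 1, a traditional “3+3” design"). A DLT is any treatment-emergent Grade 3–4 AE within 14 days of the injection, with no attribution to drug required. The rules are:

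- If "the subjects do not develop any treatment-emergent Grade 3-4 AEs (DLT"), then "the next cohort consisting of three volunteers will be included in the study to receive an escalated dose of BCD-131".
- If one of three has a DLT, three more are treated at the same dose.
- If two subjects have DLTs, "the dose of BCD-131 which resulted in these events is considered to be the maximum tolerated dose (MTD"), and escalation ends.

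SAP 3.1 carries the same rules in the same words. Neither document defines the MTD in any other way.

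Three other places bear on the point. Stage I objective 6 (protocol objectives and SAP 2.2) is: "Establish a safe dose of subcutaneous BCD-131 to be used at stage II of the study". The stage II dose is selected after stage I "Based on the comparison of pharmacokinetics, pharmacodynamics and safety of different doses of the test drug and active comparators", looking for a PD effect like that of the two reference products. In stage II, one group of six "will receive a single intravenous injection of BCD-131 at a dose established at stage I of the study", and the other group of six receives that dose subcutaneously.

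**The concern.** The plan claims a standard design but reverses the meaning of its main output. In a traditional 3+3, two DLTs among three to six subjects show that the dose is too high under the design's rule, and the MTD is then sought below it. Here the dose that triggers the stop is itself called tolerated. The rule therefore contradicts itself: toxicity is the reason to stop, yet the stopping dose receives the label that means acceptable toxicity.

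The rule matters only if two subjects at one dose have DLTs. In that case the study would state that healthy volunteers tolerate a dose at which a third or more of them had a Grade 3–4 event. Nothing in the text expressly keeps that dose out of stage II, where BCD-131 is given intravenously for the first time in this study. Stage II also has to establish the phase II doses, so a wrong MTD could be carried forward.

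**Working it through.** **Inputs.** Seven listed dose cohorts of at most six (0.05, 0.15, 0.40, 1.05, 1.70, 2.75 and 4.45 µg/kg), 12 reference-drug volunteers and 12 stage II volunteers, from the protocol's Study Design and sample size sections and SAP 3.1 and 6. The escalation rules are those set out above.

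**The plan's own figures.** 7 × 6 = 42; 42 + 12 = 54 for stage I; 54 + 12 = 66 in total. Both stated maxima reproduce. (The text introduces 8 cohorts but lists seven; 8 × 6 + 12 = 60 would not give 54.)

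**Observed event rate at a dose labelled MTD.** The label needs two DLTs in a cohort of three to six, so the smallest possible rate is 2/6 = 33%. If both occur in the first three subjects it is 2/3 = 67%. Under the usual 3+3 definition, a dose called the MTD has at most 1/6 = 17%.

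**Distance between the labelled dose and the next lower listed dose.**

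| Cohort that stops | Labelled MTD (µg/kg) | Next lower dose (µg/kg) | Ratio |
|---|---|---|---|
| 01 | 0.05 | none tested | – |
| 02 | 0.15 | 0.05 | 3.00 |
| 03 | 0.40 | 0.15 | 2.67 |
| 04 | 1.05 | 0.40 | 2.625 |
| 05 | 1.70 | 1.05 | 1.62 |
| 06 | 2.75 | 1.70 | 1.62 |
| 07 | 4.45 | 2.75 | 1.62 |

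The correction is at least one level. In the full traditional design the lower dose may itself fail once expanded to six, and in Cohort 01 no tested dose qualifies.

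**How often the rule would be triggered.** The documents give no DLT rate, so this can only be shown over a range. For a true DLT probability p at a dose, assuming escalation after 1/6 (usual, but not written in the plan):

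P(escalate) = (1 − p)³ + 3p(1 − p)² × (1 − p)³, and P(stop) = 1 − P(escalate).

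For p = 0.30: 0.343 + 0.441 × 0.343 = 0.494, so P(stop) = 0.506.

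| Assumed p | 0.05 | 0.10 | 0.20 | 0.30 | 0.40 | 0.50 |
|---|---|---|---|---|---|---|
| P(stop at that dose) | 2.7% | 9.4% | 29.1% | 50.6% | 69.1% | 82.8% |

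**Support for the lower dose.** It may have only three subjects. The one-sided exact 95% upper limit for 0/3 is 1 − 0.05^(1/3) = 63%; for 0/6 it is 1 − 0.05^(1/6) = 39%.

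**The case against.** The strongest reply is that the label decides nothing. The MTD appears only in this rule; no objective, endpoint or planned analysis uses it. Escalation stops where it should. The stage II dose is a PD match that also weighs safety, after all stage I follow-up is complete, and objective 6 requires that dose to be safe. A dose with Grade 3–4 events in a third of healthy volunteers would hardly pass. This stands, and it is why the point is minor.

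Two DLTs in six also do not prove excess toxicity. The exact 95% interval for 2/6 runs from 4% to 78%, the plan states no target rate, and DLTs need no attribution to drug. This stands too: 33% and 67% are observed event rates, the dose ratios describe the dose list and do not measure harm, and having exceeded the MTD is a verdict under the design's rule.

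Finally, the available protocol text is a synopsis, so an exclusion of the two-DLT dose might be written elsewhere. That limits the point about the missing exclusion. It does not rescue the label, which both documents state outright. A sponsor may define the MTD in its own way, but this plan invokes the traditional design and offers no other definition.

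**Conclusion.** The concern holds, as a minor error in a stated rule. If the rule is triggered, the dose named as the MTD is at least one listed level too high by the design's own convention, and a dose with an observed Grade 3–4 AE rate of 33% or more is described as tolerated. The effect within this study is limited, and the chance that the rule is triggered is unknown. The conclusion rests on reading the MTD in its usual 3+3 sense. It needs no assumed DLT rate; the assumed rates, and the assumption of escalating after 1/6, enter only the illustrative stopping probabilities.

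**What to change.** In the protocol's stage I rules and in SAP 3.1, replace the sentence on two DLTs with:

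> If two or more subjects at a dose develop DLTs, escalation stops; that dose has exceeded the MTD and is not eligible for stage II. The MTD is the next lower dose with fewer than two DLTs; if this occurs in Cohort 01, no tested dose qualifies as the MTD.

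This is a change of wording in two places. The maxima for stage I and for the whole study do not move. The downside is a lower declared MTD if DLTs occur, possibly resting on three subjects; that is acceptable while no later decision uses the MTD.

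Optionally, expand the lower dose from three to six subjects before declaring it the MTD, as the traditional design would. This fits the existing cap of six per cohort and costs up to three more volunteers and one more 14-day window.

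### As the protocol synopsis and SAP read, all six stage II volunteers given the trial's first intravenous BCD-131 may be dosed before any IV outcome is known

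*Protocol*

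**What the plan says.** **Stage I (Protocol synopsis, Study Design; SAP 3.1).** The seven listed BCD-131 cohorts, 0.05 to 4.45 µg/kg, are all subcutaneous. Entry is stepwise: "First, three volunteers will be included in Cohort 01 to receive a single subcutaneous injection of BCD-131 at a calculated starting safe dose". The next three enter only after 14 days without a Grade 3-4 event. One DLT in three adds three more volunteers at that dose. The stopping rule begins "If two subjects develop treatment-emergent Grade 3-4 AEs (DLT), the dose of BCD-131 which resulted in these events" and ends by barring further escalation. Objective 6 for stage I is: "Establish a safe dose of subcutaneous BCD-131 to be used at stage II of the study".

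**Choice of the stage II dose.** Once the last stage I volunteer has completed all procedures, an interim analysis is done. The dose is then set "Based on the comparison of pharmacokinetics, pharmacodynamics and safety of different doses of the test drug and active comparators", aiming at a PD effect similar to that of SC Mircera and Aranesp.

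**Stage II (Protocol synopsis, Study Design and Use of BCD-131 at Stage II; SAP 3.1).** Twelve volunteers are randomised 1:1. The design row reads: "Six volunteers in Group 1 will receive a single intravenous injection of BCD-131 at a dose established at stage I of the study"; the dosing row repeats this. The other six receive the same dose subcutaneously. Also: "Subjects will be asked to stay at the study site for the first 24 h after the injection". The reason given is blood sampling. Follow-up is 50 days. Neither document gives an IV sentinel, an interval between IV volunteers, a safety check partway through the IV group or an IV stopping rule.

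**The concern.** The plan is cautious where the route is subcutaneous: even at the lowest dose, three volunteers are watched for 14 days before anyone else enters. It states no such step when the route changes, although the dose is by then a pharmacologically active one. The stage I rule sits under the ascending-dose heading and its consequence is to stop escalation, so it cannot be read as covering an IV group with a single fixed dose.

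These are healthy volunteers with no therapeutic benefit to set against avoidable risk. If IV dosing caused a serious reaction often, nothing in the text would hold back the next volunteer after the first one reacted.

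**Working it through.** **1. The plan's own numbers.** Seven cohorts × 6 + 12 comparator volunteers = 54, the stated stage I maximum. Adding 12 in stage II gives 66, the stated total. The IV group is 6 of these. (The text announces eight cohorts, but seven are listed and seven reproduce 54.)

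**2. Scheme tested.** One IV volunteer is dosed first and two more after 24 h. Volunteers 4-6 follow only if the first three have fewer than two DLTs after 14 days; they are then dosed one by one at least 24 h apart. IV dosing stops at two DLTs in total. This adapts the stage I rule, which adds a second three only after one DLT. Volunteers who can be dosed before any IV outcome is known: six as written, one under the scheme. For a reaction that appears only after 24 h, three can be dosed before it is known.

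**3. Inputs.** The documents give no IV DLT rate, so p = 10%, 20%, 30% and 50% are assumptions. X is the number of DLTs, taken as independent.

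**4. Lower case: DLTs in volunteers 4-6 appear only after the next dose.** Only the check after three then works.

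- P(spare) = P(X ≥ 2 of 3) = 3p²(1−p) + p³
- Expected number dosed = 6 − 3 × P(spare)
- Expected DLTs = p × expected number dosed

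Example, p = 0.3: 3 × 0.09 × 0.7 + 0.027 = 0.216; 6 − 0.648 = 5.352; 0.3 × 5.352 = 1.61.

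**5. Best case: each DLT is evident before the next dose.**

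- P(spare) = 1 − P(X ≤ 1 of 5)
- Expected number dosed = 3 + P(X ≤ 1 of 3) + P(X ≤ 1 of 4) + P(X ≤ 1 of 5)

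Example, p = 0.3: 1 − 0.528 = 0.472; 3 + 0.784 + 0.652 + 0.528 = 4.96; 0.3 × 4.96 = 1.49.

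| True IV DLT rate | Spare ≥1, lower case | Spare ≥1, best case | DLTs if all six dosed (6p) | DLTs, lower case | DLTs, best case |
|---|---|---|---|---|---|
| 10% | 2.8% | 8.1% | 0.60 | 0.59 | 0.58 |
| 20% | 10.4% | 26.3% | 1.20 | 1.14 | 1.09 |
| 30% | 21.6% | 47.2% | 1.80 | 1.61 | 1.49 |
| 50% | 50% | 81.3% | 3.00 | 2.25 | 2.00 |

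Any additional stop decided at a safety review is not counted.

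**6. What passing the check tells us.** With 0 DLTs in 3, the one-sided 95% upper bound is 1 − 0.05^(1/3) = 63%, so it is weak reassurance.

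**7. Time.** First to last IV dose: 1 (sentinel) + 14 (check) + 2 (spacing) = 17 days as a minimum, against 0 if all six are dosed on one day. If the site would in any case space the six by 24 h (5 days), the net addition is 12.

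Calendar, taking 1176 h = 49 days, 14 days of screening per stage and no enrolment gaps:

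- No cohort expanded: 14 + 6 × 14 + 49 + 14 + 49 = 210 days; with 17 added, 227.
- All seven expanded: 14 + (6 × 28 + 14) + 49 + 14 + 49 = 308 days; with 17 added, 325.
- Left of 365 days: 138 and 40.

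**The case against.** **Absence is shown only for a synopsis and a SAP.** The protocol text available is the synopsis, and a SAP is not where sentinel rules normally sit. The basis of the calculated starting dose is also not given, so other safety text probably exists. A reader might infer that the trial has no IV safety rule at all; the documents cannot support that. This limits the point to the text seen.

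**IV toxicity is unlikely to be frequent.** The dose is matched on PD and is not chosen as the maximum. Every stage I volunteer completes follow-up before the interim. The synopsis describes Mircera, one of the closest analogues, as a solution for IV and SC injection. That does not show IV BCD-131 to be safe, but it makes the 30% and 50% scenarios unlikely. This stands, and it keeps the expected gain small.

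**Six before any outcome is a worst-case reading.** Nothing says the six are dosed together, and Day 1 is each volunteer's own study day. True: the text permits it but does not prescribe it.

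**IV exposure might be thought to exceed the SC range already tolerated.** That would depend on SC bioavailability, the chosen dose and the highest cleared cohort, none of which is known. No such exceedance is shown, and the point does not need it.

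What survives is narrow. The interim uses no IV data, and the 24 h stay, early sampling and 50-day follow-up observe people already dosed. None of them holds back a later IV volunteer.

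**Conclusion.** The point holds for the synopsis and SAP: the first IV exposure has no entry sequence and no stop, so up to six volunteers may be dosed before any IV outcome is known. It is a cheap improvement, not evidence that the planned IV dose is unsafe.

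The gain depends on the true IV DLT rate. At 10% the scheme averts only about 0.01 to 0.02 expected DLTs. At 50% it averts 0.75 (3.00 − 2.25) to 1.00 (3.00 − 2.00). Its main value is against a frequent, IV-specific reaction, and for volunteers 4-6 the larger figures require each reaction to be evident before the next dose. The results rest on assumed DLT rates, independence between volunteers and a review that always resumes dosing until the second DLT.

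**What to change.** If the full protocol already governs IV dosing, cite that rule in the synopsis and the point closes. Otherwise, before stage II opens:

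1. Randomise the 12 volunteers in two blocks of six (3 IV, 3 SC), which keeps 1:1.
2. Dose one IV volunteer first and observe for the 24 h stay already planned; then dose the next two.
3. If any IV volunteer has a Grade 3-4 AE, hold IV dosing until a documented safety review decides to resume or stop.
4. Dose IV volunteers 4-6 only after the 14-day check on the first three shows fewer than two DLTs, and space them at least 24 h apart.
5. Stop IV dosing at two DLTs in total; state that SC dosing may continue.

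**Cost.** The delay is at least 17 days plus review time; block 2 can be screened during the 14-day check. If every stage I cohort expands, the 57 days left of the 12 months (365 − 308) fall to 40 for the interim, bioanalysis, enrolment gaps, review and reporting, which is tight. Planned N stays at 66. An early stop leaves IV PK/PD on fewer than six volunteers, and replacing them or testing a lower IV dose would need N above 66.
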